9.7. Vital Signs and Physical Evaluations

Vital signs will be collected at Screening, baseline on Day 1, and continuing approximately every 6 hours until 6 hours post-parasite clearance. Vital sign measurements will include axillary temperature, systolic and diastolic blood pressure, respiratory rate, and pulse. All vital signs measurements will be presented in [Listing 20](#).

Summaries of vital signs will utilize participants' average vital signs on each study day and their respective average change from baseline. Descriptive statistics for each average vital sign parameter and its average change from baseline, including mean, SD, median, minimum, and maximum, will be presented by study day in [Table 44](#). Boxplots of average change from baseline will be presented by study day for each vital sign beginning at [Figure 238](#) and continuing through [Figure 242](#).

Physical examinations will be performed at Screening and on Day 1, Day 2, Day 3, Day 4, Day 5, Day 6, Day 7 (± 2), and Day 183 (± 14), and targeted physical examinations will be performed as needed on Day 14 (± 2) and Day 28 (± 4). Abnormal physical exam findings will be presented in [Listing 21](#).

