11.3.3 Clinical Laboratory Parameters

Hematological and biochemical laboratory parameters will be measured at study days 1, 2, 3, 4, 5, 6 and 7. Clinically relevant abnormal values based on reference intervals determined in a similar population will be tabulated and a trend analysis performed if deemed necessary.

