3.3. Study Definitions and Derived Variables

Severe Malaria

Severe malaria is defined as presence or history of fever plus a positive blood film for *P. falciparum* malaria with at least one of the following symptoms and signs:

- Repeated convulsions: More than two episodes within 24 h
- Impaired consciousness: A Blantyre coma score < 3 in children
- Coma
- Hyperpyrexia: Axillary temperature $\geq 40^{\circ}\text{C}$
- Respiratory distress: Acidotic breathing
- Inability to tolerate oral therapy and vomiting all oral intake
- Circulatory collapse or shock: Systolic blood pressure < 50 mmHg in children
- Spontaneous bleeding
- Hemoglobinuria: Hemoglobinuria presents as tea colored urine
- Jaundice
- Prostration: Extreme weakness so that the person is unable to sit, stand or walk without assistance
- Severe normocytic anaemia: Hemoglobin concentration < 5 g/dL
- Hypoglycemia: Blood or plasma glucose < 2.2 mmol/L (< 40 mg/dL)
- Renal impairment: Plasma or serum creatinine > 265 $\mu\text{mol/L}$
- Hyperparasitemia: *P. falciparum* parasitemia > 10%

Whether participants meet this definition of severe malaria will be evaluated in the process of determining enrollment eligibility. Participant history of fever, indication of positive blood film for *P. falciparum* malaria, and the presence of additional assessed symptoms and signs of severe malaria will be documented in the appropriate electronic case report form (eCRF). Only one additional sign or symptom of severe malaria must be present along with history of fever and positive blood film for *P. falciparum* malaria for a participant to meet the definition of severe malaria. Once a participant meets the definition of severe malaria, investigators may opt not to assess the participant for additional signs and symptoms. Reported symptoms and signs of severe malaria at enrollment will be summarized in [Table 6](#).

Baseline

Baseline values of primary outcome measures of physiological dysfunction, laboratory parameters, and vital signs will be defined as the most recent measurement before first dose of IV artesunate. If these measurements are not collected before first dose, such as for participants who received IV artesunate before enrollment, baseline values will be defined as either the screening measurement or the earliest measurement after first dose of IV artesunate, whichever is closest to time of first dose of IV artesunate.

Weight-for-Age and Height-for-Age Z-Scores

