9.6. Clinical Laboratory Evaluations

Biochemistry laboratory evaluations, hematology laboratory evaluations, and dipstick urinalysis will be performed at Screening and on Day 1, Day 2, Day 3, Day 4, Day 5, Day 6, and Day 7 (± 2), with serum bicarbonate additionally assessed on Day 14 (± 2) and hemoglobin additionally assessed on Day 14 (± 2) and Day 28 (± 4). Hematology laboratory evaluations will also be performed at the final study visit on Day 183 (± 14). Baseline for laboratory evaluations will be defined as given in [Section 3.3](#).

For tables, listings, and figures, the sort order for biochemistry parameters will be: alanine aminotransferase (ALT), aspartate aminotransferase (AST), blood urea nitrogen (BUN), calcium, creatinine, direct bilirubin, glucose, potassium, serum bicarbonate, serum lactate, sodium, and total bilirubin. The sort order for hematology parameters will be: hemoglobin, neutrophil count, neutrophil %, platelets, and white blood cell count (WBC). The sort order for urinalysis parameters will be: hemolyzed and non-hemolyzed blood, bilirubin, ketones, leukocyte esterase, nitrites, pH, urine glucose, urine protein and urobilinogen.

Abnormalities in clinical laboratories after the baseline visit will be captured as AEs on the appropriate data collection form and eCRF. Abnormalities that are present at baseline will only be reported as AEs after the baseline visit if they have worsened (increased in severity/grade).

All biochemistry results will be presented in [Listing 17](#), all hematology laboratory results will be presented in [Listing 18](#), and all urinalysis results will be presented in [Listing 19](#). Abnormal laboratory results will be recorded as unsolicited AEs in [Listing 16](#).

Summary statistics of measurements and their change from baseline will be presented by continuous laboratory parameter and timepoint for biochemistry ([Table 33](#)) and hematology ([Table 34](#)) parameters. Boxplots of change from baseline at scheduled collection days will be presented by weight group, sex, and timepoint for continuous chemistry parameters beginning at [Figure 221](#) and continuing through [Figure 232](#), and for continuous hematology parameters beginning at [Figure 233](#) and continuing through [Figure 237](#). Urinalysis results will be summarized by scheduled timepoint and parameter beginning in [Table 35](#) and continuing through [Table 43](#).

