14.3.4 Abnormal Laboratory Value Listings (by Participant)

Abnormal laboratory results will be listed as Unsolicited AEs in [Listing 16](#)

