14.3.6 Displays of Vital Signs

Table 44: Vital Signs Summary Statistics for Average Measurement and Average Change from Baseline by Parameter and Timepoint

[Implementation Note: Vital signs collected for each participant on each study day will be averaged over, and summary statistics will be calculated for these mean vital signs and the corresponding average changes from baseline for each participant and timepoint/study day.]

Vital signs sort order: Temperature, Systolic Blood Pressure, Diastolic Blood Pressure, Respiratory Rate, and Pulse.]

Timepoint/Study Day	N	Average Measurement				Average Change from Baseline			
		Mean	SD	Median	Min, Max	Mean	SD	Median	Min, Max
Temperature (°C)									
Baseline	X	XX.XX	XX.XX	XX.XX	XX.X, XX.X	-	-	-	-
Day 1 ^a	X	XX.XX	XX.XX	XX.XX	XX.X, XX.X	XX.XX	XX.XX	XX.XX	XX.X, XX.X
Day 2	X	XX.XX	XX.XX	XX.XX	XX.X, XX.X	XX.XX	XX.XX	XX.XX	XX.X, XX.X
Day 3	X	XX.XX	XX.XX	XX.XX	XX.X, XX.X	XX.XX	XX.XX	XX.XX	XX.X, XX.X
Day 4	X	XX.XX	XX.XX	XX.XX	XX.X, XX.X	XX.XX	XX.XX	XX.XX	XX.X, XX.X
Day 5	X	XX.XX	XX.XX	XX.XX	XX.X, XX.X	XX.XX	XX.XX	XX.XX	XX.X, XX.X
Day 6	X	XX.XX	XX.XX	XX.XX	XX.X, XX.X	XX.XX	XX.XX	XX.XX	XX.X, XX.X
Day 7	X	XX.XX	XX.XX	XX.XX	XX.X, XX.X	XX.XX	XX.XX	XX.XX	XX.X, XX.X
Day 14	X	XX.XX	XX.XX	XX.XX	XX.X, XX.X	XX.XX	XX.XX	XX.XX	XX.X, XX.X
Day 28	X	XX.XX	XX.XX	XX.XX	XX.X, XX.X	XX.XX	XX.XX	XX.XX	XX.X, XX.X
Day 183	X	XX.XX	XX.XX	XX.XX	XX.X, XX.X	XX.XX	XX.XX	XX.XX	XX.X, XX.X
[Repeat for all vital signs]									
Note: N = Number of participants in the Safety Population with the vital sign assessed at the respective timepoint or on the respective study day.									
Vital signs were collected approximately every 6 hours until 6 hours post-parasite clearance. This table displays summary statistics for the average vital signs for each participant at each timepoint or on each study day of collection.									
^a Only average post-baseline vital signs data available on Day 1 are summarized in the Day 1 row.									

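### Daily averaging of vital signs in SAP 9.7 can hide isolated temperature and blood-pressure extremes, and the Protocol 11.3.3 tabulation of abnormal laboratory values is rerouted to AE reporting without being declared

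*SAP*

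**What the plan says.** **Vital signs.** SAP 9.7 has readings taken at screening and baseline, then "continuing approximately every 6 hours until 6 hours post-parasite clearance". Its summaries use participants' "average vital signs on each study day and their respective average change from baseline". The implementation note to SAP Table 44 gives the same order of operations: "Vital signs collected for each participant on each study day will be averaged over", with summary statistics then taken over those means. Figures 238-242 show average change by study day. The individual readings go to a listing: "All vital signs measurements will be presented in" Listing 20.

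**Laboratory values.** Protocol 11.3.3 commits as follows: "Clinically relevant abnormal values based on reference intervals determined in a similar population will be tabulated". SAP 9.6 plans something different: "Summary statistics of measurements and their change from baseline will be presented by continuous laboratory parameter and timepoint for biochemistry" (Table 33) and for hematology (Table 34). The report shell at SAP 14.3.4 says "Abnormal laboratory results will be listed as Unsolicited AEs in" Listing 16. SAP 9.6 makes post-baseline laboratory abnormalities AEs, but an abnormality already present at baseline qualifies only if its severity or grade has increased.

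**Precedence and declared changes.** Protocol 11.3 lets the SAP override it. SAP Section 15 declares departures from Protocol 11.3.1 and 11.3.5 and the added power simulations. It does not mention 11.3.3.

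**The concern.** In acute severe malaria the readings of safety interest are the worst ones, and they can be brief. A mean over the day pulls one very low pressure or one very high temperature towards the child's other readings. Because the minimum and maximum in Table 44 are computed after averaging, they do not restore the lost reading.

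The laboratory issue is different. Values are not averaged within a day, so a true extreme stays visible in Tables 33-34, but the number of children outside the reference interval does not. The table promised for that purpose has no counterpart in the SAP, and a reader who relies on Section 15 for the list of departures would not learn this.

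What is at stake is how informative the safety tables are. The exposure-response analysis is not touched.

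**Working it through.** The documents give no figure on this point to reproduce. The vital-sign check is arithmetic on illustrative values; the laboratory check sets the texts side by side.

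**1. Inputs.** Readings about every 6 hours give roughly 24/6 = 4 on a full day until 6 hours after parasite clearance (SAP 9.7), and fewer on a partial Day 1 or later. SAP 3.3 states two relevant cut-offs: hyperpyrexia at an axillary temperature of 40 °C or more, and "Circulatory collapse or shock: Systolic blood pressure < 50 mmHg in children". Protocol 8.3.1 defines decompensated shock as systolic pressure below 70 mmHg in children together with impaired perfusion. The other readings (37.5 °C, 90 mmHg) are assumed.

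**2. Effect of one extreme reading.** With one reading x and k − 1 others at m, the daily mean is (x + (k − 1)m)/k.

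| One reading x | Others m | k = 2 | k = 3 | k = 4 |
|---|---|---|---|---|
| 41.0 °C | 37.5 °C | 39.25 | 38.67 | 38.38 |
| 45 mmHg | 90 mmHg | 67.5 | 75.0 | 78.75 |
| 65 mmHg | 90 mmHg | 77.5 | 81.67 | 83.75 |

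**3. Reading needed for the daily mean to reach a threshold T when k = 4.** x = 4T − 3m.

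- T = 40 °C: 160 − 112.5 = 47.5 °C.
- T = 70 mmHg: 280 − 270 = 10 mmHg.
- T = 50 mmHg: 200 − 270 = −70 mmHg, which is impossible.

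Under these inputs an isolated crossing on a four-reading day cannot appear in Table 44. With three others at 85 mmHg instead, a reading of 45 gives (255 + 45)/4 = 75 mmHg, and the mean falls below 70 only if the reading is below 280 − 255 = 25 mmHg.

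**4. Range under variation.** 400,000 child-days were simulated for each setting, with four normally distributed readings per day. All means and SDs are assumptions.

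| | Temperature ≥ 40 °C | Systolic < 70 mmHg |
|---|---|---|
| Mean; between-child SD; within-day SD | 38; 0.5-0.7; 0.6-1.0 | 95; 8-10; 8-12 |
| Child-days with any reading past T | 1.9%-16.4% | 4.4%-16.5% |
| Child-days with daily mean past T | 0.03%-1.0% | 0.3%-1.6% |
| Of days with a crossing, share also seen in the mean | 1.5%-9.3% | 4.4%-13.4% |

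The 70 mmHg column uses pressure alone, without the perfusion condition.

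**5. Whether another display supplies the count.**

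- Table 13 uses actual readings, but only one per child at each of four post-baseline timepoints (SAP 8.1), and for the PD rather than the Safety Population.
- Figures 2-4 and 24-26 plot values at those same timepoints.
- Listing 20 holds every reading. Its shell has no column linking a reading to an AE; the chemistry and hematology listings do.
- Table 6 counts the severe-malaria signs at enrollment only, and assessment may stop once one sign is met.

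**6. Laboratory route compared with the promise.**

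| | Protocol 11.3.3 | SAP |
|---|---|---|
| Unit reported | Abnormal values, tabulated | AEs, in Listing 16 and counted in Table 30 |
| Criterion | Reference intervals | Captured as an AE; DAIDS severity grading |
| Abnormal at baseline, unchanged later | Not excluded | Excluded |
| Change declared in SAP 15 | – | No |

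Tables 33-34 do not fill the gap. For example, if 5 of 80 children lose 3 g/dL of hemoglobin and 75 gain 0.5 g/dL, the mean change is (5 × (−3) + 75 × 0.5)/80 = +0.28 g/dL. The minimum shows one fall of 3 g/dL, not that there were five.

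**The case against.** A reader might infer that crossings of danger thresholds are never counted after dosing, that laboratory safety rests on distribution statistics alone, or that the abnormal-value table was dropped out of sight. The documents do not support any of these.

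- Post-baseline laboratory abnormalities are to be captured as AEs (SAP 9.6), and Table 30 counts children by system organ class, preferred term and severity. Protocol 9.2.1 also allows abnormal clinical findings to be captured as AEs.
- Table 15 gives the number of children at each Blantyre coma score at 24 h, 48 h, end of dosing and discharge.
- Urinalysis is tabulated by category (Tables 35-43), and Tables 33-34 show unaveraged extremes.
- SAP 9.6 and 14.3.4 state openly where abnormal laboratory results go, and the SAP takes precedence.

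It can also be said that four readings with three of them normal is an unfavorable case for averaging. With two readings of 90 and 45 mmHg the mean is 67.5, below 70; with one reading nothing is hidden; and a sustained abnormality moves the mean. The cut-offs are eligibility criteria, not on-treatment safety limits, and Protocol 11.3.3 promises no baseline shift table or by-day layout.

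All of this stands, and it limits the point. It does not supply a count of temperature or blood-pressure crossings. AE counts depend on reporting, and Protocol 9.2.1 prefers a diagnosis to a sign, so preferred terms need not match numeric crossings. It also leaves the change to 11.3.3 undeclared.

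**Conclusion.** Two limited defects hold. First, Table 44 and Figures 238-242 can hide isolated hypotensive or hyperpyrexic readings, and no post-baseline table counts such readings as such. Under the assumed ranges, roughly 1.5%-13% of child-days with a crossing would also show it in the daily mean. That figure rests on four readings a day and on assumed means and SDs; the direction follows from averaging before taking extremes, while the size depends on the data. Second, the Protocol 11.3.3 tabulation is replaced by AE reporting without an entry in SAP Section 15, and that route leaves out baseline abnormalities that did not worsen.

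The tempting further conclusion, that the safety report would look reassuring even if several children crossed a threshold, does not follow: Table 30, Table 15 and the listings would still carry much of that information. Neither document makes safety an outcome measure, and the primary analysis is unaffected. This is a minor-to-moderate point.

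**What to change.** - **SAP 9.7, Table 44, Figures 238-242:** add each child's daily minimum systolic and diastolic pressure and daily maximum temperature. Add the number and percentage of children with any post-baseline temperature at or above the 40 °C stated in SAP 3.3.
- **Blood-pressure count:** add it once the Protocol 8.3.1 and SAP 3.3 shock definitions are reconciled. They differ in cut-off (70 against 50 mmHg) and in whether impaired perfusion is required; this review does not say which should apply.
- **SAP 9.6:** restore the Protocol 11.3.3 table as the number and percentage of children outside the reference interval by parameter and day, naming the source of the intervals, which neither document gives. Showing baseline status is optional and goes beyond the protocol. Alternatively, declare and justify the removal in SAP Section 15.

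The cost is SAP wording and a few extra table rows or tables from data already collected, plus obtaining the reference intervals if the table is restored. Nothing changes for participants or for the primary analysis.

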9.8. Other Safety Measures

There are no other planned safety measures collected for this study.

10. PHARMACOKINETICS

Planned PK analyses, including those planned for the estimation of exposure parameters to be used in PD analyses, will be described in a separate Pharmacometrics Analysis Plan.

Individual DHA concentrations will be listed by weight group in [Listing 12](#).

11. IMMUNOGENICITY

There are no immunogenicity analyses planned for this study.

12. OTHER ANALYSES

Not applicable

13. REPORTING CONVENTIONS

P-values ≥ 0.001 and ≤ 0.999 will be reported to 3 decimal places, p-values less than 0.001 will be reported as “ <0.001 ”, and p-values greater than 0.999 will be reported as “ >0.999 ”. The mean, median, standard deviation, and other statistics will be reported to 1 decimal place greater than the original data. The minimum and maximum will use the same number of decimal places as the original data. Proportions will be presented as 2 decimal places; values greater than zero but <0.01 will be presented as “ <0.01 ”, and values less than one but >0.99 will be presented as “ >0.99 ”. Percentages will be reported to the nearest whole number; values greater than zero but $< 1\%$ will be presented as “ <1 ”; values greater than 99% but less than 100% will be reported as “ >99 ”. Estimated parameters, not on the same scale as raw observations (e.g. regression coefficients) will be reported to 3 significant figures.

14. TECHNICAL DETAILS

SAS version 9.4 or above and R versions 3.2 or above will be used to generate tables, figures, and listings.

15. SUMMARY OF CHANGES IN THE CONDUCT OF THE STUDY OR PLANNED ANALYSES

Section 11.3.1 of the Protocol Version 6.0 indicates that demographic characteristics including town/village of residence will be tabulated. Participants included in the study were to be drawn from the population of children aged 6 months to 14 years residing in Tororo District, Uganda, and were seen at Tororo Hospital. As participant town or village of residence, which was collected using a free text field, within Tororo District may vary greatly, town/village of residence will not be included in summary demographics tables but will be listed in the listing of demographic information.

Section 11.3.5 of the Protocol Version 6.0 indicates that timepoint and an interaction term between exposure and timepoint will be included in all models for the primary analysis. However, because we plan to assess the relationship of interest between the primary outcome measures using separate models for each timepoint, such terms will not be included in the primary analysis models and specification of covariance structures for repeated measures will not be necessary. Actual time of response measurement may be considered for inclusion in linear and polynomial models. Section 11.3.5 of the Protocol Version 6.0 also indicates that random effects will be included in all models for the primary analysis; while random effects will be considered for inclusion in Emax models, they are not planned for linear and polynomial models.

Expanded power simulations beyond what is presented in Protocol Version 6.0 are included in this SAP.

17. LISTING OF TABLES, FIGURES, AND LISTINGS

Table, figure, and listing shells are presented in Appendices 1, 2, and 3.

APPENDICES

9.1 Overall Study Design and Plan Description

Table 1: Study Design

Weight Groups to Determine Dosing	Study Treatment Dosing		Number of Participants
	IV Artesunate	Oral ACT	
< 20 kg	3.0 mg/kg/dose for at least 0, 12, and 24 hours	3-day course if able to transition	≤100
≥ 20 kg	2.4 mg/kg/dose for at least 0, 12, and 24 hours		

9.5.1 Pharmacodynamic, Pharmacokinetic, and Safety Measurements Assessed

Table 2: Schedule of Study Procedures

Procedures	Screening Day -1 to 1	Enrollment Day 1	Day 2	Day 3	Day 4	Day 5	Day 6	Day 7 (±2 days)	Day 14 (±2 days)	Day 28 (±4 days)	Final Study Visit, Day 183 (±14 days)	Early termination (ET) Visit
Informed consent	X											
Demographics	X											
Inclusion/Exclusion criteria	X											
Enrollment		X										
Administer IV artesunate		X	X	X								
Administer oral ACT					X	X	X					
Concomitant medication review	X	X	X	X	X	X	X	X	X	X	X	X
Physical exam	X	X	X	X	X	X	X	X	X*	X*	X	X*
Medical History	X	X										X
Vital signs***	X	X	X	X	X	X	X	X	X	X	X	X
Height	X									X	X	
Weight	X									X	X	
Thick blood smear for Pf parasitemia (per parasitemia sampling plan)	X	X	X	X	X	X						
Dried blood spot for artemisinin resistance	X											
PAXgene tube for mRNA	X											
Hematology	X	X	X	X	X	X	X	X	X**	X**	X	X^
Serum bicarbonate	X	X	X	X	X	X	X	X	X			X^
Serum lactate	X	X	X	X	X	X	X	X				X^
Serum sodium	X	X	X	X	X	X	X	X				X^
Serum potassium	X	X	X	X	X	X	X	X				X^
Serum creatinine	X	X	X	X	X	X	X	X				X^
Serum glucose	X	X	X	X	X	X	X	X				X^
Serum bilirubin, ALT and AST	X	X	X	X	X	X	X	X				X^
Urinalysis	X	X	X	X	X	X	X	X				
Blantyre coma score	X	X	X	X	X	X	X	X	X	X	X	
Pharmacokinetic assessments (per PK sampling plan)	X	X										
Neurodevelopmental assessments (parent or caregiver interview, standardized developmental, cognitive & behavioral measures)								X	X	X	X	

* Targeted physical exam, if needed

**Only hemoglobin

*** approximately every 6 h until 6 h post parasite clearance

^ If ET is before D7, collect D7 blood samples; if D8 to D14 may collect serum bicarbonate, hemoglobin, platelets, WBC count, and neutrophil count. If >D14 blood for hemoglobin, platelets, WBC count, and neutrophil count.

9.7.1 Sample Size

Table 3: Sample Size/Probability Estimates

Number of Tests	R ²	Proportion of Tests with Specified R ²	Power									
			N=100	N=90	N=80	N=75	N=70	N=65	N=60	N=55	N=50	N=45
24	0.2	0.05	0.95	-	0.88	0.84	0.80	0.78	0.72	0.66	0.6	0.52
48	0.2	0.05	0.95	-	0.88	0.84	0.81	0.76	0.69	0.63	0.56	0.49
176	0.2	0.05	-	0.93	0.88	0.85	-	-	-	-	-	-
24	0.2	0.10	0.97	-	0.92	0.89	0.86	0.83	0.77	0.72	0.65	0.58
48	0.2	0.10	0.98	-	0.92	0.90	0.87	0.84	0.79	0.73	0.66	0.58
176	0.2	0.10	-	0.96	0.92	0.90	-	-	-	-	-	-

